1 LIST OF ABBREVIATION

Abbreviation	Full Form
AE	Adverse Event
AOB	Ammonia-Oxidizing Bacteria
BID	Bis in Die (twice a day)
BP	Blood Pressure
CEA	Clinician Erythema Assessment
CRA	Clinical Research Associate
CI	Confidence Interval
CRF	Case Report Form
CTMF	Clinical Trial Master File
CTP	Clinical Trial Protocol
eCRF	Electronic Case Report Form
EOS	End of Study
ET	Early Termination
ETR	Erythematotelangiectatic rosacea
GCP	Good Clinical Practice
IB	Investigator's Brochure
ICH	International Conference On Harmonization
IEC	Independent Ethics Committee
IGA	Investigator Global Assessment
IGE	Investigator's Global Evaluation
IP	Investigational Product
IPL	Intense Pulsed Light
IRB	Institutional Review Board
ISF	Investigator Site File
IUD	Intrauterine Device
IUS	Intrauterine system
IWRS	Interactive Web Response System
LOCF	Last Observation Carried Forward
mITT	Modified Intent-To-Treat
NSAID	Nonsteroidal Anti-inflammatory Drug
OTC	Over the Counter
PP	Per-Protocol
PRN	Pro Re Nada (as needed)
PRN	Pro Re Nada (as needed)
PSA	Patient Self-Assessment
RR	Relative Risk
SAE	Serious Adverse Event
SAP	Statistical Analysis Plan
SI	Simple Imputation
SOP	Standard Operating Procedures
SUSAR	Suspected Unexpected Serious Adverse Reactions
TEAE	Treatment Emergent Adverse Event

ULN	Upper Limit of Normal Range
UPT	Urine Pregnancy Test
UV	Ultraviolet
WBC	White Blood Cell Count

2 INTRODUCTION

This document describes the statistical methods and data presentations to be used in the summary and analysis of data from Protocol RB244-001. Background information is provided for the overall study design and objectives. The reader is referred to the study protocol and electronic case report forms (eCRFs) for details of study conduct and data collection.

2.1 Study Overview

The proposed study is aimed to evaluate the safety and efficacy of B244 topical spray. A Vehicle-Controlled, Double-Blind, Multicenter, Randomized Study Design has been Selected to Evaluate the Safety and Efficacy of the B244 Investigational product in the Treatment of Mild-to-Moderate Rosacea.

There is no cure for rosacea and treatment is aimed at alleviating the symptoms. Topical or oral medications are generally prescribed for mild to moderate papulopustular rosacea. These topical medications include: metronidazole, azelaic acid, sodium sulfacetamide and sulfur, erythromycin, and tretinoin⁸. Currently these approved topical medications may cause local irritation to the skin. The oral medications prescribed for severe disease include tetracycline, doxycycline, minocycline, erythromycin and metronidazole. The systemic therapies may result in systemic adverse events such as gastrointestinal upset and photosensitivity.

It is believed, that topical application of Ammonia-Oxidizing Bacteria (AOB) will reduce survival of pathogenic bacteria present on the skin and thus improve rosacea symptoms in those affected by it. B244 is being developed as a 'live topical' to provide a natural source of AOB and NO/NO₂ to the human skin.

This is a Prospective, Vehicle Controlled, Double Blind, Multicenter, Randomized Phase II trial, Comparing the effect of twice daily B244 application for 8 weeks vs. vehicle application on treatment of mild to moderate rosacea. At Screening and Baseline all subjects must have clinical diagnosis of mild to moderate rosacea and subjects must have IGA score of 2-3 and CEA score of 2-3 to qualify for the study.

After screening and recruitment, participants will be randomized to active or vehicle application for 8 weeks. Subjects will apply a total of 4 pumps of IP per application to the face twice-a-day. Subjects will be provided with cleanser and moisturizer to use for the duration of the study. All B244 randomized subjects will be treated at the dose of 4×10^9 cells/ml via spray application.

Efficacy will be assessed using Investigator Global Assessment (IGA) score, Clinician's Erythema Assessment (CEA) score, Patient Self-Assessment (PSA) score and patient reported Skindex 16. Participant's safety will be monitored throughout the study. Safety

will be assessed by monitoring reported adverse events, vital signs, clinical chemistry and hematology and overall tolerability of the investigational product.

[figure not shown]
Approximately 130 subjects are planned to be enrolled, and assuming a 20% drop out rate, the planned overall sample size for this clinical trial is approximately 104 adult male and female subjects, 18 years of age and older with mild to moderate rosacea. Subjects will be randomized at a 1:1 ratio (B244: Vehicle) at about 8 clinical research centers in the United States.

The entire study will consist of a total of 6 visits:

- Visit 1(Day -21 to -1): Screening will occur at Days -21 to -1, followed by Washout (Days -14 to -1).
- Visit 2(Baseline/ Day 1): Randomization will occur during the baseline visit for the study (Day 1).
- Visit 3 – 5(Day 7 \pm 2 [Week 1], Day 28 \pm 2 [Week 4], Day 56 \pm 2 [Week 8]): Clinical assessments of response to treatment will be made at Week 1(Day 7), Week 4 (Day 28), and Week 8 (Day 56).
- Visit 6(Day 84 \pm 2): Subjects will come back for a 4-week post-treatment follow up visit at Week 12 (Day 84).

2.2 Study Flowchart

Figure 1. Study Flowchart

2.3 Schedule of Activities

Table 1: Schedule of Study Activities

Visit Name	Screening	Baseline/ DAY 1	Week 1	Week 4	Week 8	Week 12/ End of Study Visit	Early Termination Visit
Visit number	Visit 1	Visit 2	Visit 3	Visit 4	Visit 5	Visit 6	
Visit window in days	-21 to -1	1	7+/-2	28 +/- 2	56 +/- 2	84 +/- 2	
Informed Consent	X						
Inclusion/Exclusion Criteria	X	X					
Demographics	X						
Medical History	X	X					
Concomitant Medications	X	X	X	X	X	X	X
Physical Exam	X	X				X	X
BP & Pulse ²	X	X	X	X	X	X	X
Urine pregnancy test for WOCBP ¹	X	X	X	X	X	X	X
Clinical chemistry and hematology and urinalysis ³	X	X		X	X		X
Biomarkers ⁴		X			X		X
CEA	X	X	X	X	X	X	X
IGA	X	X	X	X	X	X	X
Skindex 16	X	X	X	X	X	X	X
PSA score	X	X	X	X	X	X	X
Telangiectasia Evaluation		X			X		X
Fitzpatrick skin type	X						
IWRS		X		X			
Dispense Investigational product to Subject ^{5/6}		X		X			
Collect Investigational product from Subject ⁵				X	X		X

Protocol: RB244-001
 Confidential

STATISTICAL ANALYSIS PLAN

 Version 2
 02-Apr-19

Visit Name	Screening	Baseline/ DAY 1	Week 1	Week 4	Week 8	Week 12/ End of Study Visit	Early Termination Visit
Visit number	Visit 1	Visit 2	Visit 3	Visit 4	Visit 5	Visit 6	
Visit window in days	-21 to -1	1	7+/-2	28 +/- 2	56 +/- 2	84 +/- 2	
Investigational product Compliance ⁵		X		X	X		X
Study Cleanser and moisturizer dispensation ⁹		X		X			
Study Cleanser and moisturizer collection					X		X
Study Diary ⁸		X	X	X	X		X
Study Counseling ⁷		X	X	X	X		
AE Collection and Assessment	X	X	X	X	X	X	X

1. Urine pregnancy test for WOCBP will be done at every visit.
2. Blood pressure readings will be obtained at every visit. Subject should be allowed to rest for more than 5 minutes sitting, then BP measurements and pulse (x3) will be performed, using the non-dominant arm with a calibrated electronic sphygmomanometer. The average of the second and third readings will be documented.
3. Subjects should fast for at least 8 hours before the test. Laboratory work includes: hematology and Lipid Panel, Albumin, Alkaline Phos, ALT, AST, Total Bilirubin, BUN, BUN: Creatinine ratio, Calcium, Chloride, Creatinine, eGFR, Glucose, Potassium, Sodium, Uric Acid, and urinalysis. HIV Ab, HCV Ab, HBsAg. will only be done at screening.
4. Subjects should fast for at least 8 hours before the test.
5. Weight of the investigational product kit will be obtained at the Baseline visit. Study staff will be asked to weigh all dispensed bottles without the carton box PRE- FIRST DOSE. Weight will be recorded in grams.
6. Subjects will be asked to bring all dispensed bottles back for the Week 4 and Week 8 visits. Upon return for the study visit, all bottles will be weighed again without the carton box. Subjects will be asked to apply the investigational product twice daily. First investigational product application will happen at the site under medical supervision.
7. Subjects will be counseled on the use of study medication and answer any questions subject may have.
8. Subjects will be asked to fill out study diary for the duration of the study.
9. Cleanser and moisturizer will be dispensed at the Baseline visit. Subjects will be asked to refrain, if possible, from using any other cleanser and/or moisturizer on their face and apply the provided product while they are participating in the trial. Any leftover moisturizer /cleanser will be collected at Week 8 visit, at which point subjects will be asked to go back to their regular routine.

3 STUDY OBJECTIVE AND ENDPOINTS

3.1 Study Objectives

3.1.1 Primary Objective

To assess the safety and tolerability of B244 applied twice daily (BID) to the face for 8 weeks in subjects with mild to moderate rosacea.

3.1.2 Exploratory Objectives

To assess the efficacy of B244 in subjects with mild to moderate rosacea.

- Proportion of subjects with IGA improvement at Week 8 relative to baseline.
- Proportion of subjects with CEA improvement at Week 8 relative to baseline.
- Change in IGA score from Baseline to Week 8.
- Change in CEA score from Baseline to Week 8.
- Proportion of Subjects with improvement in IGA or CEA at Week 1, Week 4, and Week 12.
- Change in Skindex 16 patient reported outcome from Baseline to Week 1, Week 4, Week 8, and Week 12.
- Proportion of subjects with change in PSA at Week 1, Week 4, Week 8 and Week 12 from Baseline.
- Evaluation of Telangiectasia Score at Baseline/Day 1 and Week 8

3.2 Study Endpoints

3.2.1 Safety & Tolerability (Primary)

Safety and tolerability endpoints will consist of all adverse events reported during the study duration.

3.2.2 Efficacy (Exploratory)

- Change of IGA score at Baseline to Week 1, Week 4, Week 8 and Week 12.
- Change of CEA score at Baseline to Week 1, Week 4, Week 8 and Week 12.
- Change of PSA score at Baseline to Week 1, Week 4, Week 8 and Week 12.
- Change of Skindex 16 patient reported outcome from Baseline to Week 1, Week 4, Week 8 and Week 12.
- IGA treatment success, defined as “clear” or “almost clear” with a 2-grade improvement in IGA score from baseline to the end of treatment.
- CEA treatment success, defined as “clear” or “almost clear” with a 2-grade improvement in CEA score from baseline to the end of treatment.

4 STUDY DESIGN

4.1 Summary of Study Design

This is a Prospective, Vehicle Controlled, Double Blind, Multicenter, Randomized Phase II trial, Comparing the effect of twice daily B244 application for 8 weeks vs. vehicle application on treatment of mild to moderate rosacea. We will enroll approximately 130 subjects and complete 104 subjects.

At Screening and Baseline, all subjects must have clinical diagnosis of mild to moderate rosacea and must have IGA score of 2-3 and CEA score of 2-3 to qualify for the study. After screening and recruitment, participants will be randomized to active or vehicle application for 8 weeks. Subjects will apply a total of 4 pumps of IP per application to the face twice-a-day. Randomization will be 1:1 B244 to Vehicle. Subjects will be provided with cleanser and moisturizer to use for the duration of the study. All B244 randomized subjects will be treated at the dose of 4×10^9 cells/ml via spray application. Screening will occur at Days -21 to -1. Washout will occur after Screening visit (Days -14 to -1) and randomization will occur during the baseline visit for the study (Day 1).

Efficacy will be assessed using Investigator Global Assessment (IGA) score, Clinician's Erythema Assessment (CEA) score, Patient Self-Assessment (PSA) score and patient reported Skindex 16. Clinical assessments of response to treatment will be made at Week 1 (Day 7), Week 4 (Day 28), and Week 8 (Day 56). At Baseline visit, subjects will receive a kit containing the drug product. Each bottle will be used for 2 weeks. At Week 4, subjects will return the used bottles from the kit and will be issued a new kit of drug product to be used from Week 4 through Week 8. Subjects will stop applying investigational product at Week 8 and will return investigational product at that visit. Subjects will come back for a 4-week post-treatment follow up visit at Week 12 (Day 84). Participant's safety will be monitored throughout the study. Safety will be assessed by monitoring reported adverse events, vital signs, clinical chemistry and hematology and overall tolerability of the investigational product.

Subjects would be required to discontinue the investigational product under the following circumstances:

- Development of an intercurrent illness that would jeopardize the safety, or significantly affect assessments of clinical status of a subject
- Either at the discretion of the Investigator or at the participant's request
- Development of any investigational product-related SAE
- Suspected or laboratory-confirmed pregnancy

4.2 Definition of Study Drugs

Study drug includes Test and Placebo drug products. The Sponsor will supply study drug as matching 30ml/bottle, labeled for a blinded study.

-
- Test Drug: B244, 30ml/bottle (AOBiome, LLC)
 - Placebo: Vehicle, 30ml/bottle (AOBiome, LLC)

4.3 Sample Size Considerations

Approximately 130 subjects are planned to be enrolled, and assuming a 20% drop out rate, the planned overall sample size for this clinical trial is approximately 104 adult male and female subjects, 18 years of age and older with mild to moderate rosacea. Subjects will be randomized at a 1:1 ratio (B244: Vehicle) at about 9 clinical research centers in the United States.

4.4 Study Withdrawal

A subject may voluntarily withdraw from the study at any time and for any reason without prejudice to his or her future medical care. The Investigator, Sponsor, or Medical Monitor may also withdraw a subject at any time if it is medically necessary or in the interest of subject's safety. Additional reasons for premature discontinuation of investigational product may include adverse events and major non-compliance with study procedures, as described below. The withdrawal of a subject from investigational product by the Investigator will be discussed with the Medical Monitor before the subject stops investigational product, whenever possible.

A subject will be discontinued from this study if any of the following criteria are met:

- Withdrawal of consent by the subject is received.
- In the opinion of the Investigator, Medical Monitor or Sponsor, it is not in the subject's best interests to continue in the study.
- Significant non-compliance with study procedures that would interfere with the study results or increase the subject's risks in the study, as determined by the Investigator.
- Development of an intercurrent illness that would jeopardize the safety, or significantly affect assessments of clinical status of a subject.
- Development of any investigational product-related SAE.
- Suspected or laboratory-confirmed pregnancy.

Subjects who discontinued early from the study due to lack of treatment effect after completing at least four weeks of treatment (Day 28) will be included in the mITT and PP population as treatment failures and the change in IGA and CEA from the baseline visit to the last completed visit prior to discontinuation due to lack of efficacy will be carried forward in the primary endpoint analysis. Subjects discontinued early for other reasons will be excluded from the PP population.

4.5 Early Discontinuation

If a subject discontinues prematurely, the Investigator will perform Early Termination (ET) visit, capturing the reason for discontinuation.

If a subject does not return for a scheduled visit, every effort will be made to contact the subject and document the End of Study visit assessments. The Investigator must document the primary reason for discontinuation of a study subject in the source document and on the appropriate electronic case report form (eCRF).

5 PLANNED ANALYSIS

5.1 Final Analysis

Final analysis is planned for the study after the database lock. The final analysis will follow instructions presented in this SAP.

6 GENERAL CONSIDERATION FOR DATA ANALYSIS AND HANDLING

6.1 General Summary Table and Individual Subject Data Listing

Summary tables and listings (e.g., post text tables and individual subject data listings are prepared according to ICH Guideline E3) include a “footer” providing explanatory notes that indicate as a minimum:

- SAS program name.
- Programmer.
- Date of data extraction.
- Date of output generation.

Post text tables also include reference(s) to the subject data listing(s) that supports the summary data. The data extraction date links the output to the archived database that is locked to ensure the replication of the results.

Post text tables will be organized with respect to treatment group and a column will be included to summarize all treated subjects. The order of drug presentation will be investigational drug first followed by the vehicle control. A total column will appear as the last column. The summary tables clearly indicate the number of subjects to which the data apply and unknown or not performed are distinguished from missing data.

Summary tables for medications and medical conditions are coded according the WHO Drug Dictionary. Adverse event preferred terms and body/organ systems are coded using

the MedDRA dictionary. The MedDRA dictionary can be used, as well, in the coding of signs and symptoms, medical history, physical examination abnormalities, and clinical diagnoses.

Supportive individual subject data listings, as a minimum, are sorted and presented by treatment group and subject id. Listings also include visit number, visit date, and days relative to the initiation of double-blind treatment.

6.2 General Summary Table and Individual Subject Data Listing Considerations

The default convention is to number tables and listings using a decimal system to reflect main levels of unique tables and listings and sub-levels of replicate tables and listings with two digits per level (e.g., Table XX.YY.ZZ. ...).

- The first level number should be consistent with the corresponding CSR appendix in which the tables or listings will appear. For example, the post text tables usually occupy Appendix 14 and the individual subject data listings are put in Appendix 16. All post text tables should have a main number level 14 and listings 16. The subject accounting and disposition table is usually first in the first section of the report and should be numbered Table 14.1. The supportive subject data listing would be Listing 16.1. A subset by sex 2. Subject accounting and final disposition should appear as the second level number (Table 14.1 series). Baseline and demographic profile occupy the next sub-level (Table 14.2 series). Efficacy should come next (Table 14.3 series) followed by safety Table 14.4 series). Reasons for subjects' being excluded from efficacy and protocol violation summary tables should appear as the last level (Table 14.5 series). Similar conventions should be applied to the subject data listings.
- The title should be complete, accurate, and concise. The last line of the title should provide the analysis group being summarized (e.g., Intent-to-Treat Subjects or Per-Protocol Efficacy Subjects). If possible, the units of measurement for data contained in the table can appear in parentheses to conserve space in the body of the table. For example, the summary of vital signs title could read "Summary of Sitting and Standing Blood Pressure (mmHg) and Heart Rate (bpm)." Whether in the title or body of a table or listing, units must always be specified for all appropriate data.
- If possible, variables being summarized, and statistics reported should appear in the left most column of a table. The next columns for treatment groups should report the data from left to right for the investigational drug, placebo, comparative agents, and (optional) all treated subjects, respectively.

In general, the listings should be sorted and presented by treatment assignment, investigational site, and subject number. Treatment assignment and site can appear in the banner of the listing. From left to right, the subject number, visit number, visit date, and relative day should appear.

All tables and listings must have explanatory notes that give, as a minimum, data extraction date, output generation date, complete program name and path where it is stored, as appropriate. The definition of all derived variables and decodes for coded data must appear in the notes. Due to space limitations, tables and listings may require a page of notes as a one-time preface to the output.

6.3 Data Management

Biorasi will create SDTM data sets and ADaM analysis data sets using (SAS®) software. Data analyses and summary tables are generated using SAS version 9.4 or above

6.4 Data Presentation Conventions

Continuous variables (e.g. age) are summarized using descriptive statistics (the number of subjects with available data, the mean, standard deviation (SD), median, minimum and maximum). Categorical variables (e.g. race) are summarized using counts and percentages. Percentages are calculated using the total subjects per treatment group.

The following conventions are applied to all data presentations and summaries:

- For continuous variables, all mean and median values are formatted to one more decimal place than the measured value. Standard deviation values are formatted to two more decimal places than the measured value. Minimum and maximum values are presented with the same number of decimal places as the measured value.
- For categorical variables, the number and percentage of responses are presented in the form XX (XX.X %) where the percentage is in the parentheses.
- Date variables are formatted as DDMMMYYYY for presentation. Time is formatted in military time as HH:MM for presentation.
- Wherever possible, data will be decimal aligned.
- P-values, if applicable, will be presented to 4 decimal places. If the p-value is less than 0.0001 then it will be presented as <0.0001.

Unless otherwise stated, any statistical tests performed will use 2-sided tests at the 5% significance level.

The table and listing shells and table of contents as part of this SAP provide the expected layout and titles of the tables, listings and figures. Any changes to format, layout, titles, numbering, or any other minor deviation will not necessitate a revision to the SAP nor will it be considered a deviation from planned analyses. Only true differences in the analysis methods or data handling will necessitate such documentation. The appropriate listings supporting the tables will be included and are not specified in the individual sections throughout the document.

6.5 Analysis Populations

6.5.1 Screen Failures

Investigators must account for all subjects who sign informed consent and will maintain an Enrollment Log capturing subjects screened and indicating who was enrolled or excluded and the reason why. If the subject is found not to be eligible prior to enrollment, the reason(s) for ineligibility must be documented by the Investigator.

These subjects will neither contribute to data presentations nor be included in formal statistical analyses. The number of screen failures will be included in the data disposition table. Subject Numbers assigned to subjects who fail Screening will not be re-used.

6.5.2 Safety Population

The safety population includes all randomized subjects who received investigational product.

6.5.3 mITT Population

A modified intent-to-treat population includes all subjects who are randomized, applied at least one dose of assigned product, and returned for at least one post-baseline evaluation visit.

6.5.4 Per-Protocol (PP) Population

The PP population includes all randomized subjects who met all inclusion/exclusion criteria, were compliant with the assigned study treatment, returned to the study site for the primary endpoint visit within the specified window (± 2 days) OR discontinued from the study as a treatment failure, and did not have any major protocol violations.

Subjects who administered at least 50 % of IP, have at least one baseline and post baseline in clinic visit and did not have any major protocol violations.

Subjects who discontinued early from the study due to lack of treatment effect after completing at least eight weeks of treatment should be included in the mITT and PP population as treatment failures and the change in IGA and CEA from the baseline visit to the last completed visit prior to discontinuation due to lack of efficacy should be carried forward in the primary endpoint analysis. Subjects discontinued early for other reasons should be excluded from the PP population but included in the mITT population.

The results in the mITT population will be considered definitive for superiority of each active treatment to vehicle with those in the PP population considered supportive. Safety analyses will be performed using the Safety population.

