7.4 Study Drug Exposure

At Baseline visit, Subjects will receive a kit containing (2) two 30 ml white bottles. Each bottle will be used for 2 weeks. At Week 4, subjects will return the used bottles from the kit and will be issued a new kit of two 30mL white bottles to be used from Week 4 through Week 8.

The cumulative amount of study drug exposure will be estimated by calculating the difference between the weight of the 2 bottles of drug at the time the drug was dispensed at Baseline/Week 4 and the weight of the 2 bottles at Week 4/Week 8. Differences will be summed together.

The amount of product used per day will be estimated by dividing the change by the number of days the subject was on treatment. These weights will be compared to the weight of the product that would be used if the subject was compliant with the protocol. Percent compliance will be calculated as follows:

$$\text{Percent compliance} = \left[\frac{\text{Net Weight of Study Drug}}{(1.12\text{g/day} * \text{Number of days in the study})} \right] * 100\%$$

xx.xx g

The number of days the subject administered study drug, the amount of product used, and the percent compliance will be summarized by treatment group and presented in a by-subject data listing. The subject listing will also include by-visit IP weights. Percent compliance will be calculated only for subjects who returned the study drug at the end of the treatment. In the listing, subjects who withdrew from the study early will be flagged.

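### The per-protocol population is described twice with different entry rules, and its 50% compliance criterion can lack a value for subjects who do not return product at the end of treatment

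*SAP*

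**What the plan says.** SAP v2.0 section 6.5.4 builds the PP set in three steps that are not tied together.

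- **First description.** Subjects must meet all eligibility criteria and have no major violation. They must be those who "were compliant with the assigned study treatment" (no threshold given) and who "returned to the study site for the primary endpoint visit within the specified window" of 2 days, or who discontinued as a treatment failure.
- **Second description.** A fragment with no main clause: "Subjects who administered at least 50 % of IP", who "have at least one baseline and post baseline in clinic visit", and who had no major violation.
- **Early discontinuation.** Those who stop for lack of effect "after completing at least eight weeks of treatment should be included in the mITT and PP population as treatment failures". For everyone else: "Subjects discontinued early for other reasons should be excluded from the PP population but included in the mITT population".

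SAP 4.4 sets a different duration for lack-of-effect dropouts, namely "after completing at least four weeks of treatment (Day 28) will be included in the mITT and PP population as treatment failures". The protocol carries the same pair of clauses, four weeks in 5.2 and eight weeks in 14.1.

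On compliance, SAP 7.4 divides net weight used by 1.12 g/day times days in the study, and adds: "Percent compliance will be calculated only for subjects who returned the study drug at the end of the treatment". Protocol 11.2.6.2 has bottles weighed at Day 28 as well as Day 56. Protocol 10.2.9 includes product collection and compliance at the Early Termination visit. Protocol 11.2.6.1 has every application recorded in a diary.

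The PP part of shell 14.1.1.3 lists five exclusion reasons: loss to follow-up, major deviation, less than 50% compliance, screen failure and consent withdrawal. A missing or out-of-window Week 8 visit is not among them.

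**The concern.** Two programmers working from 6.5.4 could build different PP sets, and both could defend the result from the text. SAP 6.5.4 names PP as the supportive check on mITT, and nine PP efficacy tables and six PP figures depend on it (SAP 10.1.2 and 10.3).

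If the second description governs, PP can include subjects with no Week 8 score. The main analysis does not impute (SAP 6.7.4), and percentages use all subjects in the group (SAP 6.4). PP would then drift towards mITT and lose its value as a check. Nothing downstream catches this, because SAP 7.9 tabulates data under the recorded visit even when it is out of window.

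Both descriptions also rely on compliance, and 7.4 does not produce that quantity for everyone who might need it.

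**Working it through.** **1. Membership under each rule.** I take the primary endpoint visit to be Week 8 (Day 56), where SAP 8.3 tests superiority. The window is then 56 ± 2, or Days 54 to 58. All four subjects below meet eligibility and have no major violation.

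| Subject | First description | Second description | Early-discontinuation text |
|---|---|---|---|
| At least 50% use, Week 8 visit on Day 60 | Out (60 > 58) | In | Not applicable |
| Stopped for an adverse event after 50% use, one post-baseline visit | Out (no endpoint visit, not a treatment failure) | In | Out (other reasons) |
| Stopped for lack of effect after five weeks, at least 50% use | In if counted as a treatment failure and compliant | In | In by SAP 4.4; not reached by the eight-week clause in 6.5.4 |
| Completer, Week 8 in window, bottles not returned | Needs compliance; no value | Needs 50% use; no value | Not applicable |

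The first two rows are direct contradictions. The third depends on which duration clause is followed. The fourth is the compliance gap.

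**2. The plan's own dropout figure.** 104 / (1 − 0.20) = 130, which reproduces the stated enrolment. Expected dropouts are 130 × 0.20 = 26. This is a dropout count, not a count of subjects without a compliance value.

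**3. Who could lack a needed compliance value.** Dropouts for other reasons are excluded by rule and need none. That leaves lack-of-effect dropouts and completers who do not return product. The documents give no rate for either. As an assumption, let a share s of the 26 be lack-of-effect dropouts, with none returning product:

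| s | 26 × s | Share of 130 |
|---|---|---|
| 10% | 2.6 | 2% |
| 25% | 6.5 | 5% |
| 50% | 13 | 10% |
| 100% | 26 | 20% |

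Completers who do not return bottles would be additional. Any product collected at the Early Termination visit lowers these numbers, if such a return counts as the end of treatment; 7.4 does not say.

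**4. The compliance denominator.** The daily figure agrees with the weekly one in shell 14.1.7.1: 1.12 × 7 = 7.84 g. Full use over treatment is 1.12 × 56 = 62.72 g. If days in the study run to Week 12, the denominator is 1.12 × 84 = 94.08 g.

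- A fully compliant subject then scores 62.72 / 94.08 = 66.7%.
- The 50% cut becomes 0.5 × 94.08 = 47.04 g, and 47.04 / 62.72 = 75% of planned use.

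The same section divides by days on treatment when it computes use per day, so 7.4 carries two denominators.

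**The case against.** The strongest defence is that the second description merely defines the word compliant in the first. It is a fragment, and shell 14.1.1.3 treats 50% compliance as one exclusion reason beside loss to follow-up and consent withdrawal. A stand-alone second rule would not produce those two reasons. This reading is plausible and may be what was meant. But no text links the sentences, and on this reading the fragment's visit and violation clauses would be redundant. An out-of-window visit might be recorded as a major deviation, but the SAP does not define major, and the protocol's minimum deviation list (14.3.7) does not mention visit timing.

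A reader might also infer stronger claims, which the documents do not support:

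- **That PP membership cannot be determined for up to a fifth of subjects.** The fifth is the assumed dropout rate. Most dropouts are settled without a compliance value, and product is collected at the Early Termination visit. The fifth is not a true ceiling either, since completers may also fail to return bottles. Taken literally, the sentence admitting lack-of-effect dropouts may not require compliance at all.
- **That exposure is summarised for completers only.** The restriction covers percent compliance alone. Days administered and amount used are also summarised, and shells 14.1.6 and 14.1.7.1 report weights and missed applications on the Safety population.
- **That every efficacy display is repeated on PP.** Sensitivity tables 14.2.10.1 to 14.2.10.3 are mITT only.

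Finally, PP is supportive, all efficacy is exploratory (SAP 8.3), and the primary safety analysis does not use PP. That stands, and it limits the weight of the point.

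**Conclusion.** The point holds as a drafting contradiction worth removing before database lock. The two PP descriptions classify identifiable subjects differently, the early-discontinuation sentence contradicts the second description for adverse-event stops, and the shell does not settle the matter. The compliance gap is real but narrow: it concerns completers and lack-of-effect dropouts whose product is not returned, in a number the documents do not give. The 2% to 20% range above rests on assumed shares and on no product being returned; its top end is reached only if every dropout is for lack of effect.

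The consequences are limited to the supportive PP analyses and the percent-compliance summary. The sample size, the mITT analyses and the primary safety analysis are unaffected.

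**What to change.** - **One definition in 6.5.4:** all eligibility criteria met; compliance of at least 50%, stated to be the meaning of compliant; no major violation; and a Week 8 visit within the window or treatment failure. Delete the stand-alone sentence asking for any one post-baseline visit, and align Protocol 14.1 or record the departure.
- **Shell 14.1.1.3:** add a PP exclusion reason for a Week 8 visit that is missing or out of window.
- **Section 7.4:** compute compliance from every returned kit, including those returned at Week 4 and Early Termination, over the treatment days that kit covered. Where a bottle is not returned, use the diary application count against two per day, and say what happens if the diary is missing too.
- **Denominator:** use days on treatment in 7.4 and in the footnote to shell 14.1.7.2.
- **Treatment failure:** reconcile the four-week clause (SAP 4.4, Protocol 5.2) with the eight-week clause (SAP 6.5.4, Protocol 14.1), so that one rule decides which lack-of-effect dropouts enter PP.

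The cost is SAP wording, one shell row and some programming, using data already collected. The downside is a somewhat smaller PP set and reliance on self-reported diary data for subjects who do not return bottles.
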